### 3.1.6 Randomization

Randomization will take place at the time a patient is entered On Study via RDE. Patients will be assigned to either antifungal prophylaxis with caspofungin or antifungal prophylaxis with fluconazole. Randomization will be stratified into 2 groups: 1) *de novo* AML vs. 2) all other patients.

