### 3.2.2 Diagnosis

Patients must have one of the following diagnoses and/or treatment plans:

- Newly diagnosed *de novo* AML
- First or subsequent relapse of AML
- Secondary AML
- Treatment with institutional standard AML therapy in those without AML (for example myelodysplastic syndrome, bone marrow blasts  $> 5\%$  or biphenotypia).

Please note: Patients with a history of prolonged antifungal therapy (example relapsed AML) are eligible.

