### 9.3.3 Sample size with power justification

A total of approximately 550 eligible patients will be randomized to the 2 arms (at least 275 patients on each arm). Patients will be followed for infection outcome data until criteria in Section 8.3 has been met unless the patient is off study per Section 8.2 prior to meeting criteria in 8.3.

Since the current AAML1031 proposal plans 4 courses of chemotherapy with about 1 month duration for each course, it implies that likely many study participants will be followed for IFI for about 5 months. The power calculation assumes an IFI incidence in the fluconazole group of 8% and an IFI incidence in the caspofungin treatment groups of 2% at 5 months. The hazard ratio is 0.24. We assume up to 10% of patients may have early termination of follow up on IFI due to change in AML therapy such as refractory disease, relapse, or death. It is estimated that up to 25% of patients treated on or per AAML1031 may go to SCT prior to finishing all 4 courses. Therefore, altogether up to 35% patients may not be followed until the end of 5 months for IFI. With at least 275 patients on each arm, a planned 5-month follow up on each patient and up to 35% patients being censored by 5 months, we have about 80% power to detect the expected difference in time-to-IFI curves between the 2 arms (8% vs. 2% at 5 months) in a log rank test with 2-sided alpha level of 0.05. In the calculation, both failure and censoring are assumed to follow an exponential distribution during the 5 months. The majority of the censoring events prior to 5 months are expected to be due to SCT which likely occur later in the 5 months, so the exponential censoring distribution might not be a very good approximation but should be conservative in power consideration.

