##### Analysis for Primary Objective and Secondary Clinical Objectives

The primary analysis will be based on the principle of intention to treat (i.e., by the treatment assignment of patients at randomization, regardless of subsequent compliance with the assigned treatment). Most of the events that take patients off IFI follow up prematurely such as going to SCT, relapse/refractory disease, may be considered independent from the risk for IFI; therefore they may be considered as true censoring events. Death before any such censoring events is a competing risk for IFI; however since the chance of that happening will be rare, expected to be no more than 5%, the effect of competing risk by death as the first event should be minimal. Therefore, we will focus on standard survival analyses but will also perform competing risk analyses to check if the results change after we consider death as a competing risk. In standard survival analyses, patients who go off IFI follow up before developing IFI for any reason will be treated as being censored. We will use Kaplan-Meier analyses to evaluate time to any IFI and log rank test to assess if there is any benefit associated with caspofungin compared to fluconazole. For competing risk analyses, nonparametric estimate of the cumulative incidence function for IFI will then be calculated by treating death (if first event) or possibly death plus other events as competing risk for IFI; Gray's test will be used to compare the cumulative incidence function between the 2 arms.

Similar standard survival analyses and competing risk analyses will be performed for secondary objectives 1-3 and the exploratory endpoint. For the secondary objective of time to development of invasive aspergillosis (IA), other IFI will also be considered a competing risk variable for IA in the competing risk analysis. For time to death (by any cause), only standard survival analyses will be performed. The total days of empiric antifungal therapy will also be compared between the 2 arms using t-test or Wilcoxon rank sum test.

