##### SNP Analysis in Genes Involved in Immunity

We will perform haplotype analysis using previously established methods for unrelated subjects. To deal with possible false positive or negative results, we will perform the following. First, in order to handle the concern of multiple testing, we will adjust the *P* value required for statistical significance by the false discovery rate, which is an approach to multiple testing that is a compromise between unadjusted tests of significance and more traditional, but too conservative Bonferonni adjustment. Second, to handle the potential for population stratification, all analyses will be performed with and without adjustment by ethnicity. We will use Kaplan-Meier analyses to evaluate time to any IFI, and determine

the impact of candidate gene SNPs using the log rank test. For the exploratory analysis on the relationship between IFI and the identified SNPs in the candidate genes, study participants will be grouped based on the genotype of specific SNP(s). If the primary analysis suggests no difference in IFI between caspofungin and fluconazole, standard log rank analysis will be used to compare the time to IFI between patient groups defined by the SNP(s); stratified log rank test adjusting for treatment arm will be considered if the data suggest a treatment difference on IFI between caspofungin and fluconazole.

In developing a clinical prediction model for IFI, the outcome is time to IFI and the predictors can be demographic factors, clinical factors, co-morbid conditions, and SNPs. Standard survival analysis such as Cox model (or competing risk analyses modeling the cause-specific hazard or cumulative incidence function, if needed) will be used to build predictive models. Unlike an explanatory model, inclusion of variables into the predictive model will depend only on its ability to improve the prediction of the outcome and does not necessarily have to be based on biologic plausibility (although plausibility could make a prediction rule more accessible to clinicians). On the other hand, a clinically useful predictive model also needs to be practical in that the variables must be available in most clinical settings. We will take into account these factors in developing the predictive models, and internal cross-validation techniques will be considered in assessing the models.

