#### 9.3.5 Interim Monitoring

Study data will be reviewed by DSMC twice a year during the first 2 years of study activation, and once a year thereafter upon their approval if the study goes smoothly. We plan two formal interim efficacy analyses comparing treatment outcomes between the 2 arms, after approximately one third and two thirds of the patients have completed study treatment and IFI observation. The endpoints for the interim analyses include time to the following individual event: IFI, invasive aspergillosis, death. Log rank test will be the primary method for these interim analyses; monitoring boundary for the primary endpoint on IFI will be based on Lan-Demet's method with spending function at . Competing risk analyses such as estimating the cumulative incidence of the event and Gray's test for IFI or IA will be performed as well to check that corresponding competing risk analyses do not suggest a different conclusion than the standard survival analyses.

Informal interim safety analyses will also be performed at each DSMC review on the observed adverse events between the 2 arms. This analysis will include all patients who receive at least one dose of study medication. The proportion of patients experiencing any grade 4 or higher non-hematological adverse event will be compared between the 2 groups using chi-square tests. For this monitoring, each test will be at two-sided level of 0.05 without adjustment for multiple testing, to ensure us being alerted by any potential difference in adverse events between the 2 arms. If a significant difference between the 2 arms is found ( $p < 0.05$ ), the study committee will examine the adverse event profiles for safety considerations and decide if any action needs to be taken.

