### 13.8 Statistical Design

#### 13.8.1 Sample Size and Estimated Event Rates

The parent trial comparing prophylaxis with caspofungin to fluconazole in newly diagnosed AML patients anticipates enrollment of at least 275 patients for each arm with a total cohort of approximately 550 patients. As noted above we anticipate that at least 80% of the patients enrolled in the parent trial will also be enrolled in this ancillary study. This will result in 220 patients from each study arm. Consent for testing will be included as a part of the parent trial enrollment, thus significantly limiting the need for additional resources to complete this biomarker study.

The estimated number of probable or proven IFI events for final analyses will be different for both proposed biomarkers as they account for different types of fungal infections and the incidence for each will vary by study arm. The Fungitell Assay has the potential to identify most pathogenic fungi and thus a majority of the probable or proven IFIs will be considered as true events (excluding IFIs from *Zygomycetes* and *Cryptococci*). The Platelia *Aspergillus* EIA is specific for *Aspergillus* and thus only probable or proven IA will be considered as true events for that analysis.

Based on Section 9.3.3 of the parent trial the estimated incidence of IFI for patients in the fluconazole group is 8% and 2% in the caspofungin arm. Assuming the enrollment of 220 patients in each study arm, there would 18 IFI events in the fluconazole group and 4 IFI events in the caspofungin group. Based on data from the CCG 2961 AML trial, one-third of microbiologically proven fungal infection were the result of *Aspergillus*. Therefore, it is estimated that 6 of the 18 IFI events in the fluconazole group will be IA and between 1 and 2 of the IFI events in the caspofungin group will be IA.

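### The primary and interim IFI tests do not use the de novo versus other stratum applied at randomization; the plain tests are valid, and stratifying them is a small improvement at almost no cost

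*Combined protocol and SAP*

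**What the plan says.** Sections 3.1.6, 4.1.1 and 9.1 all state that "Randomization will be stratified into 2 groups", namely de novo AML and everyone else.

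The analysis sections do not take this factor up:

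- **Primary analysis (9.3.4):** "We will use Kaplan-Meier analyses to evaluate time to any IFI and log rank test to assess if there is any benefit". No stratum is named.
- **Competing-risk check (9.3.4):** Gray's test "will be used to compare the cumulative incidence function between the 2 arms". Again no stratum.
- **Interim analyses (9.3.5):** "Log rank test will be the primary method for these interim analyses", applied to IFI, invasive aspergillosis and death.
- **Power (9.3.3):** computed for the comparison "in a log rank test with 2-sided alpha level of 0.05", with no mention of strata.

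The only stratified log-rank test in the document is in the SNP analysis of 9.3.4, where a "stratified log rank test adjusting for treatment arm will be considered" under a condition. Its stratum is treatment arm, not diagnosis.

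**The concern.** When randomization is balanced within strata, the usual practice is to compare arms within those same strata. The plan sets up the stratum and then does not use it. Because the SNP section says stratified where it means that, the natural reading of the primary and interim tests is that they are unstratified.

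Two things are at stake, both modest.

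1. **Precision.** If the stratum predicts IFI, balanced randomization makes the plain test slightly conservative, so a little power is given away. The stratum could plausibly be prognostic. The other group mixes relapsed AML, secondary AML and non-AML diagnoses, and section 3.2.2 adds that "Patients with a history of prolonged antifungal therapy (example relapsed AML) are eligible".
2. **Prespecification.** The design expects only about 22 IFI events and has two formal interim looks, so a few events can decide significance. The plain and stratified tests sometimes disagree. Which one counts should be settled before anyone sees data.

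**Working it through.** **Inputs from section 9.3.3.** 275 patients per arm; IFI risk 8% versus 2% at 5 months; exponential failure and censoring; 35% censored by 5 months; two-sided alpha 0.05.

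**Reproducing the plan's figure.**

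- Hazard ratio = ln(0.98)/ln(0.92) = 0.242, matching the stated 0.24.
- Monthly hazards: fluconazole −ln(0.92)/5 = 0.01668; caspofungin −ln(0.98)/5 = 0.00404; censoring −ln(0.65)/5 = 0.08616.
- Probability of an observed event = λ/(λ+μ) × [1 − exp(−5(λ+μ))], where λ is the failure hazard and μ the censoring hazard. Fluconazole: 0.1622 × (1 − 0.65 × 0.92) = 0.0652, or 17.9 events in 275. Caspofungin: 0.0448 × (1 − 0.65 × 0.98) = 0.0163, or 4.5 events. Total 22.4.
- Events needed for 80% power (Freedman) = (1.960 + 0.842)² × [(1 + 0.242)/(1 − 0.242)]² = 21.1, so 22 whole events. That corresponds to about 540 patients, against 550 planned.
- Power with 22.4 events = Φ(√22.4 × 0.758/1.242 − 1.96) = 82.3%; with 22 events, 81.6%. Allowing for the two interim looks, with the spending function read as αt² (an assumption, because the symbol is garbled in the text), it is 80.7%.

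The stated power of about 80% is confirmed, and it belongs to the plain log-rank test.

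**Plain against stratified, same simulated trials.** Stratum shares and stratum risks are not in the documents and are assumed. Arms are balanced within stratum, overall fluconazole risk is held at 8%, and the hazard ratio and censoring are the same in both strata. The grid uses shares of 90/10, 75/25 and 60/40, with the smaller stratum at higher risk, and 20,000 trials per setting. The standard error is about 0.25 points for power and 0.15 points for null rejection.

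| Risk ratio between strata | Power, stratified minus plain | Null rejection, plain | Null rejection, stratified |
|---|---|---|---|
| 1 | within 0.1 points | 4.9–5.0% | 4.9–5.0% |
| 2 | +0.1 to +0.2 | – | – |
| 4 | +0.5 to +0.6 (75/25: 86.2% to 86.7%) | 4.5–4.7% | 4.8–5.0% |
| 7.7 (extreme) | +0.9 to +1.9 (75/25: 85.7% to 87.1%; 90/10: 85.2% to 87.1%) | 3.7–4.5% | 4.9–5.2% |

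Simulated power is a few points above the Freedman value for both tests. The comparison between tests is what matters here. They reach different decisions in 0.3% to 2.9% of trials.

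**Separate simulation.** 25,000 trials per setting, with 10% or 30% of patients in the other group and its hazard 0.5 to 8 times that of de novo patients. Stratified minus plain power was −0.1 to +0.2 points for relative hazards 0.5 to 2, +0.1 to +0.5 at 4, and about +0.9 at 8. Null rejection was 4.1–5.3% plain and 5.0–5.3% stratified. The tests disagreed in 0.2% to 2.2% of trials. A further run gave +0.5 to +0.7 points at ratio 4 and +1.2 to +1.6 at 7.7, with no loss when censoring differed by stratum.

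**Few events.**

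- *First interim*, 92 per arm, about 22.4/3 = 7.5 events. At nominal 0.05 (for comparison only) with 75/25 strata, the change is −0.2 points at ratio 1 and +0.9 at ratio 4. At the αt² level of 0.05 × (1/3)² = 0.0056, it is −0.1 to 0.0 points at ratio 1 and +0.7 at ratio 4.
- *Invasive aspergillosis.* Section 13.8.1 says "one-third of microbiologically proven fungal infection were the result of" Aspergillus, so a risk of 8%/3 = 2.67% is used, again giving about 7.5 events. The change is +0.1 points at ratio 1 and +0.6 at ratio 4.
- Stratified null rejection was 4.8–5.1% at nominal 0.05 for both the interim and the aspergillosis settings.

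**The case against.** The strongest reply is that nothing is broken. The plain log-rank test is valid, errs on the safe side if at all, and is the test the trial was powered for, so design and analysis agree. The gain is close to zero unless the strata differ in IFI risk several-fold, and nothing in the documents supports a ratio of 4 or more. Section 3.2.2 shows that the other group is mixed, not how its risk compares. Sections 3.2.5 and 3.2.7 also exclude patients with IFI in the previous 30 days or under IFI treatment. Gray's test and the death endpoint were not simulated, and the main scenarios assume one hazard ratio common to both strata.

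Most of this stands. The benefit is small and conditional. Stratifying cannot be said never to cost anything: with about 7.5 events and no prognostic difference there is a loss of 0.1 to 0.2 points. The simulation results apply to the log-rank test only. Competing deaths are expected in no more than 5% of patients, so Gray's test should behave similarly, but that is reasoning and not a result.

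The objection does not remove the case for acting. The plan stratifies randomization and is then silent on whether its tests follow, and the two tests do not always agree. Stating the choice costs a sentence.

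**Conclusion.** The point holds, as a modest improvement and not as a flaw in validity. The randomization stratum is absent from the primary log-rank test, the interim log-rank tests and Gray's test. No stated figure in the plan changes, and the primary conclusion is not threatened.

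Stratifying brings null rejection back to about 5% where the plain test would fall as low as 3.7%. It needs no extra patients and no extra alpha. The power gain ranges from nothing at risk ratios up to 2 to at most 1.9 points in an extreme case, and the largest loss in the settings above is 0.2 points. All gains depend on assumed stratum sizes and risks, and on a common hazard ratio across strata. The firmer reasons for the change are consistency with the randomization and fixing the test in advance.

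**What to change.** In 9.3.4 and 9.3.5, name the primary and interim IFI test as a log-rank test stratified by the randomization factor (de novo AML versus all other patients). Make the competing-risk check a Gray's test stratified by the same factor. Keep the unstratified log-rank test as a prespecified sensitivity analysis. Use the same stratified wording for the time-to-event comparisons of invasive aspergillosis and death. The t-test or Wilcoxon comparison of days of empiric therapy need not change.

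The cost is SAP wording only. The factor is already recorded at randomization, and the sample size, alpha and stated power stay as they are.

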## 8.0 CRITERIA FOR REMOVAL FROM PROTOCOL THERAPY AND OFF STUDY CRITERIA

### 8.1 Criteria for Removal from Protocol Therapy

- a) Development of proven or probable IFI including IA according to institutional diagnosis.
- b) Patients who begin conditioning for HSCT.
- c) Begin a new chemotherapy regimen for AML that is refractory to, or relapsed with current AML chemotherapy.
- d) Refusal of further protocol therapy by patient/parent/guardian.
- e) Recovery from neutropenia following completion of the final planned AML chemotherapy course .
- f) Physician determines it is in patient's best interest.

Patients who are off protocol therapy are to be followed until they meet the criteria for Off Study below. Follow-up data will be required unless consent was withdrawn. A patient that is placed on empiric fungal therapy for prolonged fever and neutropenia should NOT be removed from protocol therapy for subsequent AML chemotherapy courses unless one of the off protocol therapy criteria is met.

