##### Secondary Endpoints

Endpoints for secondary objectives include: the development of proven or probable IA defined according to criteria developed by the EORTC/MSG (from which time to IA will be computed), death due to any cause (from which time to death will be computed), the need for empiric antifungal therapy defined as the institution of antifungal therapy while a study subject is receiving prophylaxis (from which the days of empirical antifungal therapy will be computed), results from GM and beta-D glucan assays for the diagnosis of IFI or IA alone, and results of the genotyping assays for SNP analysis.

An exploratory endpoint will be the development of proven, probable or possible IFI.

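### For time to empiric antifungal therapy (objective 1.2.3) Kaplan-Meier leads and the competing events are not fixed, so 1 minus Kaplan-Meier would exceed the share of patients who actually start it

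*Combined protocol and SAP*

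**What the plan says.** Section 9.3.1 defines the third secondary clinical endpoint as the need for empiric therapy, "defined as the institution of antifungal therapy while a study subject is receiving prophylaxis". The quantity it derives from this is days of empiric therapy.

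Section 9.3.4 then adds time-to-event methods: "Similar standard survival analyses and competing risk analyses will be performed for secondary objectives 1-3 and the exploratory endpoint". The model is the IFI analysis earlier in that section. Standard survival analysis is the focus, with this rule: "In standard survival analyses, patients who go off IFI follow up before developing IFI for any reason will be treated as being censored". Competing-risk analysis is there to see whether the result changes. Its cumulative incidence function is obtained by "treating death (if first event) or possibly death plus other events as competing risk for IFI", and Gray's test compares the arms.

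The section adapts this model for two of the three secondary objectives. For IA, other IFI is added as a competing event. For death, only standard survival analysis is used. For time to empiric therapy nothing is added. Total days of empiric therapy are also compared, by t-test or Wilcoxon test.

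Section 8.1 ends protocol therapy at, among other events, "Development of proven or probable IFI including IA according to institutional diagnosis" (a), "Patients who begin conditioning for HSCT" (b) and the start of a new AML regimen (c). Section 8.3 ends IFI observation at (b) and (c) but does not list IFI. Section 9.3.3 expects that "altogether up to 35% patients may not be followed until the end of 5 months for IFI".

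**The concern.** Censoring suits a patient who could still have the event unseen. Here, once protocol prophylaxis has ended for conditioning, a new regimen or IFI, the event as defined can no longer happen. Kaplan-Meier treats such a patient as if the later risk matched that of patients still on prophylaxis. It then estimates the risk in a hypothetical cohort in which nobody leaves prophylaxis for these reasons.

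The plan defends censoring at transplant and relapse by independence from the risk of IFI. It makes no such argument for empiric therapy. Even if independence held, 1 minus Kaplan-Meier would still answer the hypothetical question.

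At stake is the reported percentage needing empiric therapy in each arm, and the absolute reduction credited to caspofungin. If the check used death alone, it would seem to confirm the Kaplan-Meier figure.

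**Working it through.** **The plan's own figures first.** Under the exponential model of section 9.3.3, the hazard ratio is ln(0.98)/ln(0.92) = 0.0202/0.0834 = 0.242 (stated: 0.24). With 275 per arm and 35% exponential censoring, about 17.9 + 4.5 = 22.4 IFI events are expected. Freedman's formula gives power Φ(√22.4 × (1 − 0.242)/(1 + 0.242) − 1.96) = 82%, against the stated figure of about 80%. These inputs are therefore read as the plan intends. The plan has no figure for empiric therapy.

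**Inputs**
- Exits by 5 months: up to 35%, of which transplant up to 25% (9.3.3).
- Death as first event: no more than 5% (9.3.4).
- IFI at 5 months: 8% versus 2% (9.3.3).
- Empiric therapy at 5 months by 1 minus Kaplan-Meier, p: not in the documents. Assumed 20% to 70%, with constant hazard.

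**Even exits.** Cumulative hazards over 5 months are h_e = −ln(1 − p) for empiric therapy and h_c = −ln(1 − c) for the competing events. The share who actually start is

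CIF = h_e/(h_e + h_c) × (1 − exp(−(h_e + h_c))).

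For p = 50% and c = 35%: h_e = 0.693, h_c = 0.431, and CIF = 0.693/1.124 × (1 − exp(−1.124)) = 41.6%. With death only, h_c = −ln(0.95) = 0.051 and CIF = 48.9%.

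**Late exits, form A:** all 35% leave at constant hazard in months 3 to 5. With λ = h_e/5 and μ = −ln(0.65)/2,

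CIF = 1 − exp(−3λ) + exp(−3λ) × λ/(λ + μ) × (1 − exp(−2(λ + μ))).

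**Late exits, form B:** 35% leave uniformly over months 2.5 to 5. CIF is the integral of λ exp(−λt) G(t) over 0 to 5 months, where G is 1 up to month 2.5 and then falls linearly to 0.65.

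| Assumed 1−KM | CIF, even exits (excess) | CIF, late A (excess) | CIF, late B (excess) | CIF, death only (removed) |
|---|---|---|---|---|
| 20% | 16.4% (3.6) | 18.6% (1.4) | 18.4% (1.6) | 19.5% (0.5) |
| 30% | 24.7% (5.3) | 28.0% (2.0) | 27.7% (2.3) | 29.3% (0.7) |
| 40% | 33.1% (6.9) | 37.5% (2.5) | 37.1% (2.9) | 39.1% (0.9) |
| 50% | 41.6% (8.4) | 47.1% (2.9) | 46.6% (3.4) | 48.9% (1.1) |
| 60% | 50.3% (9.7) | 56.9% (3.1) | 56.2% (3.8) | 58.7% (1.3) |
| 70% | 59.3% (10.7) | 66.8% (3.2) | 66.1% (3.9) | 68.6% (1.4) |

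For scale, the simulated standard error of the Kaplan-Meier estimate in one arm of 275 is 3.2 to 3.5 points.

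**Absolute difference, illustration only.** Assume 50% (fluconazole) versus 40% (caspofungin) by Kaplan-Meier, and treat IFI (8% versus 2%) as a further exit:
- Even exits: 40.2% versus 32.8%, a difference of 7.4 points instead of 10.0. The ratio is 0.82 instead of 0.80.
- Late exits, form B: 45.0% versus 36.8%, a difference of 8.3 points.
- Death only: 48.9% versus 39.1%, a difference of 9.8 points.

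If the empiric-therapy hazards are equal, the difference in IFI alone opens a gap of only 0.4 to 1.2 points between the arms (assumed 20% to 60%, even exits).

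**The case against.** The strongest reply is that the remedy is already planned. The sentence that brings in Kaplan-Meier also commits to competing-risk analyses, and their model allows events beyond death. A reader might infer that the check is confined to death; the text does not say so. What stands is that the other events are optional and unnamed, so the set could be chosen after the data are seen, and Kaplan-Meier leads.

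A reader might also infer that patients are censored at IFI. The written rule concerns leaving IFI follow-up, and section 8.3 does not list IFI. No rule is set for empiric therapy at all. Transplant and new regimens, the larger group, appear in both 8.1 and 8.3 and do not depend on this inference.

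The claim that the event becomes impossible needs prophylaxis to mean protocol prophylaxis. That is the natural reading, but section 9.3.1 does not state it. Treatment begun on prophylaxis for a suspected infection later classified as IFI might itself count as the event.

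Finally, objective 1.2.3 is comparative, section 9.3.1 derives days of therapy, and nowhere is 1 minus Kaplan-Meier announced as the headline figure. This is fair, and it limits the point to the absolute percentages that a Kaplan-Meier analysis would naturally produce.

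**Conclusion.** The point holds in a limited form. If prophylaxis means protocol prophylaxis, 1 minus Kaplan-Meier for time to empiric therapy exceeds the share of patients who actually start it. The excess is about 1 to 4 points if exits come late, which section 9.3.3 expects for transplant, and about 4 to 11 points if they are even. Both ranges rest on an assumed 20% to 70% by Kaplan-Meier, a constant empiric-therapy hazard and the plan's ceiling of 35% exits. At 20% to 60%, death as the sole competing event accounts for only about 0.5 to 1.3 points.

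A reader might go further and conclude that the comparison of the arms is invalid. It is not: the log-rank test still compares cause-specific hazards, and in the illustration the ratio barely moves. Nor do the documents fix how far the absolute difference would be overstated, because that needs empiric-therapy rates they do not give.

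This is more than missing detail, because the method named to lead does not estimate the share of patients who start empiric therapy, and the check that would correct it is left open. It should be changed, though it concerns a secondary endpoint.

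**What to change.** In section 9.3.4, after the sentence on IA, state that:

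- for time to first empiric antifungal therapy, the competing events are institutional proven or probable IFI, start of HSCT conditioning, start of a new AML regimen and death, each if it comes before empiric therapy;
- the cumulative incidence by arm, with Gray's test, is the reported absolute estimate for objective 1.2.3;
- the log-rank test is kept as the cause-specific comparison, and 1 minus Kaplan-Meier is not reported as the incidence of empiric therapy.

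Two rules should be settled at the same time: whether antifungal treatment started on prophylaxis for a suspected infection later classified as proven or probable IFI counts as an empiric-therapy event; and how other ends of prophylaxis, namely refusal and physician decision (8.1 d and f), are handled.

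The cost is a few sentences. Treatment, follow-up and sample size do not change. The events named are those already used to apply sections 8.1 to 8.3, so their dates should be available, although the case report forms are not in the documents and this should be confirmed. The downside is a slightly smaller reported incidence and absolute difference.
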